#### 3. Proportion of subjects with $\geq$ grade 3 bleeding

This analysis will be identical to that conducted for Secondary Endpoint number 1 except proportions for each study arm will be calculated based on the number of subjects with grade 3 or higher bleeding.

**4. Proportion of subjects with PLT refractoriness defined as 2 sequential transfusion episodes, each with CCIs < 5000 measured 1 hour post-transfusion.**

PLT refractoriness is defined as 2 sequential transfusion episodes with CCIs < 5000 measured 1 hour post-transfusion for the transfusion episode. The count increment (CI) is calculated as follows:  $CI = \frac{(Post-transfusion[1\ hour] PLT (PLTs/\mu L) - Pre-transfusion PLT (PLTs/\mu L))}{Number\ of\ PLTs\ in\ component\ (PLTs)\ (\times\ 10^{11})}$ .

Typically, the platelet count is expressed in platelets/ $\mu$ L.

The CCI is calculated using the following equation considering a single transfusion episode at a time:

$$CCI = \frac{(Post-transfusion[1\ hour] PLT (PLTs/\mu L) - Pre-transfusion PLT (PLTs/\mu L)) \times BSA (m^2)}{Number\ of\ PLTs\ in\ component\ (PLTs)\ (\times\ 10^{11})}$$

$$\text{where, } BSA (m^2) = 0.007184 \times \text{Height (cm)}^{0.725} \times \text{Weight (kg)}^{0.425}$$

$$\text{where, Number of PLTs in component (PLTs)}(\times 10^{11}) = \text{Platelet yield}$$

$$\text{and where, Platelet yield} = [\text{Platelet Concentration (}10^6/\mu\text{L)} \times \text{Platelet Unit Volume (mL)}]/100$$

If the full transfusion volume was not transfused the partial volume transfused will be use in this calculation. The platelet concentration remains unchanged, regardless of volume transfused.

The value for the number of platelets transfused (infused dose) is always expressed in multiples of  $10^{11}$ .

If two successive CCIs < 5000 measures are not observed, then PLT refractoriness is not attained. Based on these criteria among the patients in the mITT population, the proportion of subjects who experience PLT refractoriness for the MIRASOL ( $\pi_T$ ) and CONTROL ( $\pi_C$ ) groups are defined as:

$$\pi_T = \frac{\text{Number of Subjects with positive PLT refractoriness (Test Arm)}}{\text{Total Number of Subjects in the Test Arm}}$$

$$\pi_C = \frac{\text{Number of Subjects with positive PLT refractoriness (Control Arm)}}{\text{Total Number of Subjects in the Control Arm}}$$

The difference between the MIRASOL and CONTROL arms ( $\pi_T - \pi_C$ ) will be reported along with the 95% CI about this difference. Negative values of the reported difference favor the MIRASOL group. A test of the null hypothesis that this difference is zero will be carried out by Fisher's exact test.

NOTE: The pre-transfusion episode platelet count closest and prior to the transfusion episode should be used for all CCI calculations. The pre-transfusion episode platelet count should be collected within 24 hours of the start of the transfusion episode to be clinically meaningful in relation to the effect of the

transfusion on the post-transfusion platelet count. The post transfusion platelet count to calculate the 1-hour CCI is measured by a platelet count between 10 minutes and  $\leq 4$  hours post-transfusion episode. The post transfusion platelet count to calculate the 24-hour CCI ( $\geq 18$  but  $< 30$  hours post-transfusion episode) is measured by a platelet count within the defined window post-transfusion episode.

**5. Immune PLT refractoriness will be subjects with PLT refractoriness as defined above and who also have a positive antibody test within 14 days before or after the onset of PLT refractoriness**

Blood System Research Institute will assume all analytic responsibilities for this analysis. Details are provided in Appendix II.

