- All tables will clearly indicate the sample sizes contributing to the summary data in the column heading and labeled as “*Treatment* (N=)”. For example, if a table reports data for the Full Analysis Set (FAS) population, N would represent all subjects in the FAS. If a table reports data for the Safety Set (SS), N would represent all subjects in the SS. Within the table the small “n” will represent the number of subjects within the population of interest who have non-missing data or data otherwise available for the summary measures of interest (i.e. the denominator for a subset of the overall population being presented in the summary). If no data are available for a TFL, the output will be produced with “No data to display”. Footnotes which are data driven may be applied to the TFLs as needed. These changes will not necessarily be made to the mock TFLs.
- Percentages are calculated out of the header N unless otherwise footnoted.
- Duration of periods of time will be calculated in days as (stop date – start date + 1) in order to include both the starting day and final day of the periods of time. Conversions to weeks, months, or years will be calculated as days/7, days/30.4375, or days/365.25, respectively.
- In general, missing values will be handled as follows: for continuous variables at baseline, missing values will be excluded from calculation of summary statistics and the n of subjects reporting will be reported. For categorical values at baseline, the number and percent of subjects with missing values will be displayed. Handling of missing postbaseline values will depend on the analysis.

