### **7.4.1. Dropouts and Missing Data**

Handling of subject dropouts and other forms of missing data with regard to the primary endpoint will be discussed in Section 8.1. Handling of subject dropouts and other forms of missing data with regard to key secondary endpoints is the responsibility of BSRI. No imputation of missing data will be applied to secondary, exploratory or safety endpoints unless otherwise specified.

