### **7.5.2. Modified Intent-to-Treat Analysis Set**

The mITT analysis set is defined as containing all randomized subjects who undergo at least one (1) study transfusion post-randomization based on the treatment group to which they were randomized. Subjects will be analyzed according to the treatment group (MIRASOL or CONTROL) they were assigned at randomization.

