For the primary outcome of days of grade 2 or higher bleeding first a basic summary table will be presented of the average days of grade 2 or higher bleeding, and the average days of bleeding assessments per treatment group. Then a summary of estimates from the negative binomial model with the natural log of the estimate, standard error, and 95% CI will be presented. Last, a table testing the non-inferiority hypothesis will be included showing the estimate of MIRASOL versus CONTROL from the model, the natural log of the NI margin, standard error, and 95% CI.

The mean CCI at 1 hour (measured between  $\geq 10$  minutes and  $\leq 4$  hours) and the mean CCI at 24 hours (measured between  $\geq 18$  and  $< 30$  hours) after the end of every transfusion episode, when possible, will be calculated for each subject, and the mean of each treatment group will be presented along with differences in means for each pairwise comparison (treatment-control) at each time point (1 hour and  $> 18-30$  hours) as discussed in the analysis of Secondary Endpoint # 9. This will also be presented by age group (age  $< 18$ , 18-65 and  $> 65$  years) and treatment type (allogeneic transplant, autologous transplant, and chemotherapy).

Additionally, HLA antibody results are captured in a central laboratory database and will be maintained exclusively by BSRI. Blood System Research Institute will be responsible for reporting HLA results by treatment, age group, and treatment strata to the DMC.

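### The platelet refractoriness endpoint scores subjects with missing 1-hour CCIs as not refractory, so the proportion is understated whenever those CCIs are missing

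*SAP*

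**What the plan says.** SAP Section 8.2.2, item 4 gives the event: "PLT refractoriness is defined as 2 sequential transfusion episodes with CCIs < 5000 measured 1 hour post-transfusion for the transfusion episode". It then sets the default for everyone else: "If two successive CCIs < 5000 measures are not observed, then PLT refractoriness is not attained". The Protocol document carries the same text.

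The denominator is the whole arm: "Based on these criteria among the patients in the mITT population, the proportion of subjects who experience PLT refractoriness" is computed over all subjects in each arm. The mITT set (Section 7.5.2) is described as "containing all randomized subjects who undergo at least one (1) study transfusion post-randomization". The general convention in Section 7.4 agrees: "Percentages are calculated out of the header N unless otherwise footnoted".

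On missing data, Section 7.4.1 states: "No imputation of missing data will be applied to secondary, exploratory or safety endpoints unless otherwise specified". Item 4 specifies no exception. The 1-hour value "is measured by a platelet count between 10 minutes and" 4 hours after the episode, so a count taken outside that window yields no 1-hour CCI. Item 4 does not say how an episode without a valid 1-hour CCI is handled.

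The rule reaches two other endpoints. Exploratory endpoint 4 (Section 8.3) repeats the analysis with a cutoff of 7500. Secondary endpoint 5, immune refractoriness, builds on the item 4 definition and is analysed by the HLA laboratory group under Appendix II.

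**The concern.** Failing to observe an event is not the same as observing that it did not happen. A subject with several transfusion episodes but no usable 1-hour CCIs has unknown status, yet enters the proportion as not refractory. The plan says it will not impute secondary endpoints, but this rule acts as a single imputation of the favourable outcome, because a lower proportion in MIRASOL is read as favouring MIRASOL.

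Two errors can follow, depending on the pattern of missing counts:

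- **Equal missingness in both arms:** both proportions fall, the absolute difference shrinks and power drops. A real excess in the MIRASOL arm would be harder to see.
- **Unequal missingness:** the arm with more missing counts looks better, which can create, hide or reverse a difference.

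The planned output does not report how many subjects could be classified, so a reader could not tell whether either had happened.

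**Working it through.** The plan states no refractoriness rate, missing-CCI rate or power for this endpoint, so there is no figure to reproduce. The calculations below show direction and scale only.

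**Inputs from the plan.** Event: two consecutive episodes with 1-hour CCI < 5000. Denominator: all mITT subjects in the arm. Size: about 558 mITT subjects randomized 1:1 (Section 6.3.3), so 558 / 2 = 279 per arm. Test: Fisher's exact test.

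**Assumptions.** True refractoriness rates and missing fractions are chosen for illustration. Each 1-hour CCI is missing independently with probability m. Each refractory subject has exactly one qualifying pair. The test is taken as two-sided at 0.05, because item 4 states no level.

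**Step 1: share of true cases still detected.** Both CCIs of the pair must be present, so the share is (1 − m)²:

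| m | (1 − m)² |
|---|---|
| 10% | 0.81 |
| 20% | 0.64 |
| 30% | 0.49 |
| 40% | 0.36 |

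**Step 2: equal true rates of 20%, unequal missingness.** The reported proportion is 0.20 × (1 − m)².

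- MIRASOL, m = 20%: 0.20 × 0.64 = 12.8%.
- CONTROL, m = 10%: 0.20 × 0.81 = 16.2%.
- Apparent difference: 12.8 − 16.2 = −3.4 points, where the truth is 0.

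With 279 per arm, simulation (20,000 replicates) gives about a 17% chance of a significant result favouring MIRASOL. With m = 10% in both arms that chance is about 2%.

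**Step 3: a true excess, 25% MIRASOL vs 15% CONTROL.**

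- m = 20% in both arms: 0.25 × 0.64 = 16.0% vs 0.15 × 0.64 = 9.6%. The difference is 6.4 points instead of 10, and simulated Fisher power falls from 82% to 58%.
- m = 30% vs 10%: 0.25 × 0.49 = 12.25% vs 0.15 × 0.81 = 12.15%. The difference all but disappears.

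**Step 4: relaxing the one-pair assumption.** Subjects were simulated with 1 + Poisson episodes and a subject-specific probability of a low CCI (60,000 subjects per setting), scoring consecutive episodes.

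- Mean 4 episodes, true rate about 15%: reported 12.8%, 10.6%, 8.5% and 6.7% at 10%, 20%, 30% and 40% missing.
- Mean 6 episodes, true rate about 20%: reported 15.2% at 20% missing and 10.0% at 40% missing.

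The loss is milder than in Step 1 because some subjects have more than one qualifying pair, but the direction is the same. With no CCIs missing there is no bias.

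**The case against.** The strongest reply is that nothing shows 1-hour counts will often be missing. Section 8.2.2, item 9 describes only the 18-to-30-hour count as optional and attaches its worry about sparse data to that count, which suggests that 1-hour counts are expected routinely. The Section 8.6 statement that CCIs "after the end of every transfusion episode, when possible, will be calculated for each subject" concerns an interim table and covers both time points, so it is weak evidence about the 1-hour count. This stands: the size of the bias is unknown and could be small.

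The endpoint is also one of ten additional secondary endpoints, which Section 7.4 treats as supportive. Endpoint 9 analyses 1-hour CCIs directly in a mixed model without scoring missing values as good. Both points limit the consequence; neither corrects the scoring rule.

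Some stronger readings are tempting but not supported:

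- *The plan contains two contradictory definitions.* For low / missing / low, a reader might think that the sentence on successive CCIs allows refractoriness while the consecutive-episode definition does not. That sentence says only when refractoriness is not attained. It is a necessary condition and fits the definition. The case deserves a clarification, not a finding of contradiction.
- *The result will favour MIRASOL.* No text indicates that counts will be missed more often in either arm.
- *Refractoriness is the main signal of platelet function.* No section says so.

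Finally, one could object to replacing the mITT analysis with determined subjects only. That is right: the set is defined after randomization, and it need not recover the true rate. In a separate simulation (mean 4 episodes, 20% missing), a true 14.6% was reported as 10.4% under the plan's rule and 12.8% among determined subjects.

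**Conclusion.** The point holds as a conditional statement. The plan's explicit rule classifies unknown status as absence of refractoriness over the full mITT denominator, and it provides nothing that would reveal or bound the effect. Whenever 1-hour CCIs are missing, the expected proportion is too low. The treatment difference is then diluted if missingness is equal, or shifted in favour of the arm with more missing counts if it is not.

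The size cannot be fixed from the documents. The −3.4 point illustration rests on an assumed true rate of 20%, an assumed 20% vs 10% missing, independence, and one qualifying pair per case. With complete counts the problem disappears. It should be corrected because the correction is cheap and two further endpoints inherit the rule, but it does not touch the primary conclusion.

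**What to change.** Keep the mITT comparison in Section 8.2.2, item 4 and add the following, ideally before final unblinding:

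1. **Event.** State that two adjacent episodes must both have a measured 1-hour CCI below the cutoff. This settles low / missing / low: it is not an observed event.
2. **Classification.** *Refractory*: the event is met. *Not refractory*: fewer than two episodes, or every adjacent pair contains at least one measured CCI at or above the cutoff. *Undetermined*: everyone else.
3. **Reporting.** Show the number and percentage undetermined by arm.
4. **Sensitivity analyses.** (a) Compare refractory with not refractory among determined subjects. (b) Give mITT bounds. With R refractory and U undetermined among N subjects, an arm's proportion lies between R/N and (R + U)/N. The difference MIRASOL (T) − CONTROL (C) lies between R_T/N_T − (R_C + U_C)/N_C and (R_T + U_T)/N_T − R_C/N_C. Under the adjacent-episode rule, the plan's own figure is the lower limit R/N in each arm.
5. **Linked endpoints.** Apply the same rules to exploratory endpoint 4 at its 7500 cutoff, and pass the three categories to the group analysing secondary endpoint 5.

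The cost is SAP wording, one derived variable and a few table rows. The determined-only set is defined after randomization and the bounds are wide if many subjects are undetermined, so both belong beside the mITT result rather than in place of it. If counts are nearly complete, the bounds close up around the mITT figure.

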**6. Number of PLT transfusion episodes per subject, i.e., frequency of transfusion**

The analytic approach used to investigate secondary endpoint # 6 will be based on a negative binomial model. The total number of PLT transfusion episodes (regardless of whether or not the transfusion is determined to be “off-protocol”) will be calculated for each subject, and the negative binomial model will include only the covariate for treatment group which will give a regression coefficient; the exponentiated regression coefficient is an estimate of the ratio of the transfusion rate for the treatment groups. The offset in the negative binomial model will be the natural log of time in days from Day 0 to transfusion independence, study dropout or end of the 28-day treatment period for each subject.

**7. Days of PLT support; the number of days from the first to the last PLT transfusion**

The number of days from the first to the last PLT transfusion will be analyzed using a Cox regression model with the treatment group serving as the lone covariate. Subjects will be censored at Day 27 or on their last study visit in the treatment period. Reported results will consist of the hazard ratio along with the corresponding 95% CI and p-value. A hazard ratio greater than 1 will favor the MIRASOL group because it will correspond to a shorter duration of platelet support. A KM plot contrasting the two study arms will also be generated to provide a visual representation of survival probability as a function of study duration.

**8. Platelet utilization rates (average number of PLTs transfused)**

The platelet utilization rate will be calculated for each individual by adding the number of platelets transfused ( $10^{11}$ ) during the treatment period divided by the total number of transfusion units for each individual. The number of PLTs transfused will be included regardless of whether or not the transfusion is determined to be “off-protocol”.

The difference between the platelet utilization rate received in the MIRASOL ( $\mu_T$ ) and CONTROL ( $\mu_C$ ) groups will then be estimated as  $\mu_T - \mu_C$ , and a test of equality will be carried out using a pooled t-test. A 95% CI for  $\mu_T - \mu_C$  will also be reported; negative values of  $\mu_T - \mu_C$  favor the MIRASOL group in the sense that it reflects a lower average number of platelets required in support of care.

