### 1. Total number of units of PLTs transfused/day of PLT support

For each subject, the number of units (a PLT unit is defined as one [1] single PLT bag) will be totaled and divided by that subject's number of days of PLT support. Consequently, each subject will have a value for the total number of PLT transfusion units started per day of PLT support. A day of PLT support is defined as any day in which a study PLT transfusion was started. Transfusions lasting more than twenty-four (24) hours will be counted as multiple days of PLT support. These values will then be averaged across subjects and will be displayed for each treatment group (MIRASOL vs CONTROL).

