### 2. Total number of PLTs (PLT dose) transfused/Body Surface Area/day of PLT support

For each subject and transfusion episode, the PLT dose, i.e. the number of PLTs in a component (as defined in the denominator of the CCI equation), will be divided by the subject's baseline BSA which is calculated using the following equation:

$$\text{BSA (m}^2\text{)} = 0.007184 \times \text{Height (cm)}^{0.725} \times \text{Weight (kg)}^{0.425}$$

Similar to the analysis of the First Exploratory Endpoint, this value will be divided by the number of days that subject received PLT support. These values will then be averaged across subjects and displayed for each treatment group (MIRASOL vs CONTROL).

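### Secondary endpoint 8, labelled platelet utilization, measures platelets per bag and cannot show whether fewer platelets were required

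*SAP*

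**What the plan says.** SAP section 8.2.2, item 8, builds the endpoint in two steps. The numerator: "The platelet utilization rate will be calculated for each individual by adding the number of platelets transfused" over the treatment period, with off-protocol transfusions included. The sum is then "divided by the total number of transfusion units for each individual". For the comparison of arm means, "a test of equality will be carried out using a pooled t-test", with a 95% CI for the MIRASOL minus control difference. Negative values are said to "favor the MIRASOL group in the sense that it reflects a lower average number of platelets required in support of care". The list in section 6.3.2 names the endpoint as the average number of platelets transfused, with no per-unit qualifier. The document labelled Protocol carries the same text.

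Two exploratory endpoints in section 8.3 also concern platelet use. Item 1 is units per day of support, where "a PLT unit is defined as one [1] single PLT bag" and "A day of PLT support is defined as any day in which a study PLT transfusion was started". Item 2 is platelet dose per body surface area, and "this value will be divided by the number of days that subject received PLT support". Both are descriptive.

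**The concern.** A utilization endpoint should rise when a subject needs more platelets. Dividing by the subject's own number of units removes the part of use that depends on how many transfusions were needed. What is left describes the product, not the demand for it.

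The stated direction adds to the problem. If MIRASOL bags hold fewer platelets than control bags, the endpoint would be reported as favoring MIRASOL whatever the total consumption, even if subjects needed extra bags to make up for the lower content. A reader of the results table would take a line labelled platelet utilization as evidence on total use.

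The plan measures use differently elsewhere. Endpoint 10 counts red cell units per subject with a time offset and calls lower values lower utilization. Endpoint 6 counts platelet episodes per subject with a time offset. Item 8 is the exception.

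**Working it through.** The plan gives no expected value, SD or power for this endpoint, so there is no figure to reproduce. The check is algebra, then worked examples, then a simulation.

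**Algebra.** Let a subject receive k bags with mean transfused content d (x10^11).

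- Total platelets used = k x d.
- Endpoint 8 = (k x d)/k = d, for any k.
- Ratio of total use between arms = (ratio of units) x (ratio of content).
- When the content ratio is below 1, endpoint 8 always favors MIRASOL. Total use is nevertheless higher on MIRASOL once the units ratio exceeds 1/(content ratio): 1/0.95 = 1.05, 1/0.90 = 1.11, 1/0.85 = 1.18.

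Reading units as episodes gives dose per episode, with the same problem. The section's CCI rule uses the volume actually transfused, so d is best read as platelets transfused per bag, not the content of a full bag.

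**Worked examples.** All contents and counts are assumptions. Control is 4 bags x 4.0 = 16.0.

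| MIRASOL | Total | Endpoint 8 difference | Total-use ratio |
|---|---|---|---|
| 6 x 4.0 | 24.0 | 4.0 - 4.0 = 0.0 | 24.0/16.0 = 1.50 |
| 6 x 3.6 | 21.6 | 3.6 - 4.0 = -0.4 | 21.6/16.0 = 1.35 |
| 5 x 3.8 | 19.0 | 3.8 - 4.0 = -0.2 | 19.0/16.0 = 1.19 |

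The error can also count against MIRASOL. MIRASOL at 5 x 4.0 = 20.0 against control at 10 x 3.5 = 35.0 gives an endpoint 8 difference of +0.5, although MIRASOL uses 15.0 fewer.

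**Exploratory endpoints.** Take the first row above, one unit per transfusion day and a BSA of 1.9 m2. Exploratory 1 is 4/4 = 1.0 against 6/6 = 1.0. Exploratory 2 is 16.0/1.9/4 = 2.105 against 24.0/1.9/6 = 2.105. Neither moves, although total use is 50% higher, because each added transfusion day raises numerator and denominator together.

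**Simulation.** The arm size is 558/2 = 279, from the 558 mITT subjects in section 6.3.3. Everything else is assumed: units per subject are 1 + gamma-mixed Poisson (shape 2), with mean 4 in control; unit content is normal with mean 4.0 in control, within-subject SD 0.6 and between-subject SD 0.3. Pooled t-tests are two-sided at 0.05, with 1,000 trials per row.

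| MIRASOL mean units, content | Endpoint 8 difference | Significantly favors MIRASOL | Total-use ratio | Total significantly higher |
|---|---|---|---|---|
| 6, 4.0 | 0.00 | 2.6% | 1.50 | 100% |
| 5, 4.0 | 0.00 | 2.0% | 1.25 | 95% |
| 6, 3.8 | -0.20 | 100% | 1.42 | 100% |
| 6, 3.6 | -0.40 | 100% | 1.35 | 99.8% |
| 5, 3.8 | -0.20 | 99.9% | 1.19 | 86% |
| 5, 3.6 | -0.40 | 100% | 1.13 | 52% |

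With equal content and 50% more units, endpoint 8 was significant in either direction in 5% of trials, which is the chance level. A repeat with 4,000 trials per row agreed within about 2 percentage points, except for 5 x 3.8, where total use was significantly higher in 82%. That is the safer figure.

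**The case against.** The strongest reply is that higher use would probably be seen elsewhere. Endpoint 6 tests the episode rate in the mITT set with off-protocol transfusions included, and endpoint 7 tests duration of support. Under the assumptions above, a simple count-ratio test standing in for endpoint 6 (no offset modelled) flagged higher MIRASOL use at least as often as a test of total platelets: 97% against 82% for 5 x 3.8, 97% against 50% for 5 x 3.6, and 100% for both at 6 x 4.0. Section 7.13 also plans platelet exposure summaries in the mITT and Safety Sets. This stands, and it limits the harm. It does not make endpoint 8's own reading correct. Episodes are not platelets, endpoint 7 measures time, and the exposure summaries are descriptive.

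Exploratory 1 and 2 do respond if extra use means more units on the same days. Item 7 also defines days of support differently, as first to last transfusion. Under either definition they are descriptive rates, not total use.

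The simulated percentages are soft. For 5 x 3.8, the chance of detecting higher total use falls to roughly 61 to 65% with gamma shape 1 and about 40% with shape 0.5. The chance that endpoint 8 favors MIRASOL falls to about 65% with between- and within-subject SDs of 0.8 and 1.0. The algebra needs none of these figures.

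Finally, endpoints come from CIP version 9.0, which is not among the documents, so a per-unit average may be intended. If so, the label and the directional statement are still wrong for it.

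**Conclusion.** The concern holds. As defined, endpoint 8 is mean platelets transfused per bag and does not respond to the number of bags a subject needed. This follows from the plan's own formula and requires no assumption. The statement that a lower value "it reflects a lower average number of platelets required in support of care" is therefore unsupported.

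Whether the sign would oppose total use in this trial is unknown, because it depends on platelet content and unit counts by arm, which the documents do not give. At a content ratio of 0.90, 11% more units on MIRASOL is the break-even point; beyond it, the endpoint favors MIRASOL while total use is higher.

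The consequence is limited. Section 7.4 treats secondary outcomes as supportive and exploratory, and the primary non-inferiority conclusion does not depend on this endpoint. It should be corrected because it attaches a prespecified direction of benefit to a quantity that cannot carry it.

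**What to change.** Redefine endpoint 8 as total platelets transfused (x10^11) per mITT subject over Day 0 to 27, from recorded on- and off-protocol transfusions. Report the difference or ratio between arms with a 95% CI. Keep the present ratio, if wanted, as mean dose per unit, and delete the sentence that negative values favor MIRASOL. Renaming the ratio and deleting that sentence is the minimum correction, but it would leave total platelet use without an endpoint.

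The plan must then settle three details:

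- **Observed time.** Dropout or early death lowers a raw total. A rate over observed days through Day 27 would allow for this. An offset that stops at transfusion independence, as in endpoint 6, would partly absorb extra use caused by longer dependence.
- **Transfusions after independence.** Section 7.7 ends the treatment period at transfusion independence if that comes before Day 27. The plan should say whether later transfusions up to Day 27 are captured and counted.
- **Skew.** Total use is likely to be skewed, so the pooled t-test may need a log-scale or robust alternative.

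The cost is small: SAP wording and one derived variable. The total is essentially the numerator already planned, apart from the period after independence, and platelet yields are already needed for CCI. If the CIP defines the endpoint per unit, its wording would need to change as well.
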